### **Data Collection Processes**

The Al-Quds Committee for Ethical Considerations approved this study (REF.13/24). Consent forms were distributed to students, and their approval was sought before data collection began.

The researcher trained five dentists to conduct interviews and dental examinations, ensuring the data collection process was standardised and calibrated. Training sessions for the data collectors were held every 15 days throughout the research period to maintain consistency and accuracy in data collection.

During the baseline phase, all participants were provided with a comprehensive explanation of the study. Baseline data were collected in March 2024. The selected participants were randomly divided into intervention and control groups, ensuring that both groups were matched by age and gender. The control group received one oral educational session, while the intervention group participated in six sessions. The educational sessions were held every 10 days over two months.

After two months of interactive education, participants were re-examined and interviewed. Follow-up data were collected in the same schools using the same dental examination measures and questionnaires used during the baseline phase.

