Statistical Analysis Plan (SAP)

Official Title: Effectiveness of an Interactive School-Based Oral Health Education Program in Reducing Periodontal Disease Among Palestinian Adolescents: A Double-Blind Intervention Study

NCT Number:

Document Date: March 1, 2024

Sponsor: Al-Quds University

Overview

This Statistical Analysis Plan outlines the statistical methods and procedures used to analyse data for the intervention study assessing the effect of a school-based oral health education program on periodontal conditions and related behaviours among 9th-grade students in Nablus City, Palestine.

Study Objectives

- Primary: To evaluate the effectiveness of the intervention on CPITN and S-OHI scores.
- Secondary: To assess changes in oral hygiene practices, dietary habits, and smoking behaviours.

Data Preparation and Management

Data were entered into IBM SPSS Statistics version 25.0.

All data were reviewed for completeness and consistency prior to analysis.

Normality testing was conducted using Shapiro-Wilk tests.

Missing data was minimal and handled by complete case analysis.

Statistical Analyses

Descriptive statistics will be used to summarise baseline characteristics by group (mean \pm SD, frequencies, percentages).

- Paired t-tests will be used to assess within-group differences from baseline to post-intervention.
- Independent t-tests were used to compare mean differences between the intervention and control groups.
- Statistical significance was set at $p < 0.05$.
- Confidence intervals were calculated at the 95% level for all primary outcomes.

Study Questions VS Analysis Plan

1. Can interactive educational sessions reduce **Community Periodontal Diseases Index** scores among 9th-grade students in Nablus City for two months?

1. Data Type and Variables

Dependent Variable: Community Periodontal Index for Treatment Needs (CPITN) **score** → Continuous quantitative variable

Independent Variable: Group type (Intervention vs. Control) → Binary categorical variable

Time Points: Pre-intervention (baseline)

Post-intervention (after two months) → true experimental design (pre-post measurements)

2. Statistical Design

Since there are two time points and two groups, the analysis includes:

A. Within-Group Analysis (Intervention group and control group):

Purpose: To assess whether there is a significant reduction in CPITN scores after the interactive educational sessions within the two groups themselves.

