Test to use: Paired t-test, as the data is normally distributed.

B. Between-Group Analysis (Post-intervention comparison):

Purpose: To compare the post-intervention CPITN scores between the intervention and control groups.

Test to use: Independent T-test as the data is normally distributed

Note: The two groups were examined for their differences in baseline measurement.

2. Can interactive educational sessions reduce **S-Oral hygiene index scores** among 9th-grade students in Nablus City within two months?

1. Data Type and Variables

Dependent Variable: Simplified Oral Hygiene Index (S-OHI) score → Continuous quantitative variable

Independent Variable: Group type (Intervention vs. Control) → Binary categorical variable

Time Points: Pre-intervention (baseline)

Post-intervention (after two months) → true experimental design

2. Statistical Design

Since there are two time points and two groups, the analysis includes:

A. Within-Group Analysis (Intervention group only):

Purpose: To assess whether there is a significant improvement (reduction) in S-OHI scores after the interactive educational sessions.

Test to use: *Paired t-test*, as the data is normally distributed.

B. Between-Group Analysis (Post-intervention comparison):

Purpose: To compare the post-intervention S-OHI scores between the intervention and control groups.

Test to use: *Independent t-test*, as the data is normally distributed

3. Will oral hygiene practices, smoking habits, and dietary habits improve among 9th-grade students after interactive educational sessions are applied in Nablus City?

Questionnaire responses related to oral hygiene practices, dietary habits, and smoking behaviour were **recoded** into scale variables to facilitate the computation of mean scores pre-and post-intervention. Correct answers reflecting preventive behaviours, in line with American Dental Association (2023) guidelines, were assigned the highest scores, while incorrect responses received the lowest scores, for example:

- "Do you clean your teeth?": Yes = 1, No = 0
- "How often do you clean your teeth?": Once/day = 1, Twice/day = 2, Three times/day = 3
- "How long does it take to clean your teeth?": One minute = 1, Two minutes = 2, More than two minutes = 3, Don't know = 0
- "Brushing technique": Scrubbing = 1, Bass = 2, Modified Bass = 3
- "Toothbrush type": Hard bristle = 1, Soft bristle = 2, Medium bristle = 3

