"Toothbrush replacement frequency": Every three months = 1, Two months = 2, Monthly = 3

Additional coding schemes are provided at the end of this document. The overall mean differences in oral hygiene practices, dietary habits, and smoking behaviour scores were then compared between groups using independent sample t-tests, with sub-analyses conducted for each behavioural domain separately. Statistical significance was set at $p < 0.05$.

1. Data Type and Variables

Dependent Variables (Behavioural Scores):

- **Oral hygiene practices score** → Continuous quantitative
- **Smoking habits score** → Continuous quantitative
- **Dietary habits score** → Continuous quantitative

Independent Variable: Group type (Intervention vs. Control) → Binary categorical

Time Points: Pre-intervention (baseline)

Post-intervention (after two months) → True experiment design (pre-post)

2. Statistical Design

Since the question involves **multiple behaviours** and **two time points**, the analysis will be conducted separately for each behavioural domain:

A. Within-Group Analysis (Intervention Group Only)

- **Purpose:** To evaluate if there was a significant improvement in each behaviour **after the intervention**.
- **Test to use:** Paired t-test for:
 - Oral hygiene practices score

- Dietary habits score
- Smoking habits score

(Assumes normal distribution)

B. Between-Group Analysis (Post-Intervention Comparison)

- **Purpose:** To compare post-intervention behavioural scores between intervention and control groups.
- **Test to use:**
 - **Independent t-test** for:
 - Oral hygiene practices
 - Dietary habits
 - Smoking behavior

(Assumes normal distribution)

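### Between-arm tests compare post-intervention scores without adjusting for the baseline score collected on every measure, and an undefined second wording (mean differences) leaves the primary comparison unclear

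*SAP*

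**What the plan says.** **Question-specific text.** Under Question 1, part B of the SAP, the purpose is "To compare the post-intervention CPITN scores between the intervention and control groups". Under Question 2, part B, it is "To compare the post-intervention S-OHI scores between the intervention and control groups". Under Question 3, part B, it is "To compare post-intervention behavioural scores between intervention and control groups". In each case the test is an independent t-test, and no covariate is named.

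**General text.** The SAP's Statistical Analyses list says "Independent t-tests were used to compare mean differences between the intervention and control groups". The recoding paragraph under Question 3 says "The overall mean differences in oral hygiene practices, dietary habits, and smoking behaviour scores were then compared between groups using independent sample t-tests". Neither place defines the differences. Question 3 therefore carries both wordings for the same behaviour scores.

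**Use of baseline.** Baseline values enter through descriptive summaries, within-group paired t-tests, and a note under Question 1: "The two groups were examined for their differences in baseline measurement". The note states no consequence if a difference is found. Neither document mentions ANCOVA, regression, a mixed model or a group-by-time term.

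**Availability of baseline.** The protocol (Data Collection Processes) says "Follow-up data were collected in the same schools using the same dental examination measures and questionnaires used during the baseline phase". On allocation, the same section says "The selected participants were randomly divided into intervention and control groups", while the sample-size text under Table 1 speaks of intervention schools and control schools.

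**The concern.** Two things are at stake.

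The first is precision. When the same measure is taken before and after, part of the post-intervention score is predictable from the baseline score. A comparison of post scores alone leaves that part in the error. Put another way, it carries r times any chance baseline difference between the arms into the estimated effect. Checking the arms for baseline differences does not remove this.

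The second is which test counts. If the undefined phrase means changes from baseline, the SAP holds two different between-arm tests for the same outcomes and does not say which is primary. The two respond in opposite directions to a chance baseline difference. With no true effect and a baseline difference of D, the post-only estimate is expected to be off by rD and the change-score estimate by -(1 - r)D. A plan that leaves both open allows the choice to be made after the results are known.

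**Working it through.** **Inputs from the documents.** 536 intervention and 410 control students, 15 schools (protocol, text under Table 1). These counts are taken as given: the stated dz = 0.5, alpha 0.05 and 90% power give 44 pairs two-sided, not 946 students, but that is a separate matter and nothing below depends on it. The plan gives no figure of its own for the gain from baseline adjustment.

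**Assumed inputs.** The documents give neither the baseline/post correlation r nor the intraclass correlation (ICC) for schools. I use r = 0.3, 0.5, 0.7 and ICC = 0.01, 0.05, 0.10, with r the same in both arms.

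**1. Independent students.** Variance of the between-arm difference relative to the post-only t-test is 1 - r² for baseline adjustment. For change scores it is 2(1 - r) if SDs are equal at both visits.

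| r | Post-only | Change score | Baseline-adjusted | Adjusted vs post-only | Adjusted vs change |
|---|---|---|---|---|---|
| 0.3 | 1 | 1.40 | 0.91 | -9% | -35% |
| 0.5 | 1 | 1.00 | 0.75 | -25% | -25% |
| 0.7 | 1 | 0.60 | 0.51 | -49% | -15% |

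The standard error of the post-only difference is sqrt(1/536 + 1/410) = 0.0656 SD. The difference detectable with 90% power, two-sided, is (1.960 + 1.282) × 0.0656 = 0.213 SD. Multiplying by sqrt(1 - r²) gives 0.203, 0.184 and 0.152 SD with adjustment. For an illustrative effect of 0.2 SD, power is 86.2% post-only, and 89.2%, 94.1% and 99.0% adjusted.

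**2. Chance baseline difference.** Its SD is sqrt(DE × (1/536 + 1/410)), with design effect DE = 1 + (m - 1) × ICC and m = 946/15 = 63.07.

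| Allocation | DE | SD of baseline difference | Carried error, r = 0.3 to 0.7 |
|---|---|---|---|
| Students | 1 | 0.066 | 0.020 to 0.046 |
| Schools, ICC 0.01 | 1.62 | 0.084 | 0.025 to 0.058 |
| Schools, ICC 0.05 | 4.10 | 0.133 | 0.040 to 0.093 |
| Schools, ICC 0.10 | 7.21 | 0.176 | 0.053 to 0.123 |

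Carried error is r times the SD of the baseline difference; the school rows assume the same relation between and within schools. This is the loss in step 1 seen from another side, not an additional one. For students at r = 0.5, (0.5 × 0.0656)² = 0.00108, which is 25% of 0.0656² = 0.00430.

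**3. If schools were allocated.** The step 1 figures no longer apply. For a school mean, let v = ICC + (1 - ICC)/m be its variance and c = rb × ICC + rw × (1 - ICC)/m its baseline/post covariance, where rb and rw are the between-school and within-school correlations. With adjustment slope b, the variance ratio adjusted/post-only is (v + b²v - 2bc)/v. With ICC 0.05 and rw = b = 0.5 (all assumed), v = 0.05 + 0.95/63.07 = 0.0651.

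| Between-school correlation rb | 0.8 | 0.5 | 0.2 | 0 |
|---|---|---|---|---|
| Adjusted / post-only | 0.52 | 0.75 | 0.98 | 1.13 |

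The ratio is 1 when c = bv/2 = 0.0163, that is, at rb = (0.0163 - 0.0075)/0.05, about 0.17. Below that, adjusting for the student's own baseline score loses precision.

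**4. Only if the undefined phrase means change scores.** With no true effect, the post-only and change-score z statistics correlate sqrt((1 - r)/2) = 0.59, 0.50, 0.39. The chance that at least one exceeds 1.96 in absolute value is 8.8%, 9.1% and 9.4% (simulation, 4 million draws each; independent students, equal SDs), against a nominal 5%.

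**The case against.** The strongest reply is that nothing here is invalid. Under random allocation a t-test of post scores is unbiased, and baseline adjustment is only an efficiency gain. That stands, and it limits the weight of the point.

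It can also be said that 946 independent students leave little to gain: for a between-arm difference of 0.5 SD, power already exceeds 99.99%. That is correct for effects of that size. But the protocol's 0.5 is a paired effect size, so it does not establish that a between-arm difference that large is expected. For smaller effects, and for the width of the interval, the gain remains.

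The gain is least certain where precision would matter most. If schools were allocated, step 3 shows that adjustment may do almost nothing or slightly harm, and clustering itself matters more: at ICC 0.05 the design effect is 4.10. This stands. Clustering is a separate issue and adds no weight to this one.

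Every size rests on assumed inputs. Equal SDs at both visits are doubtful for an index limited to scores 0 to 2 in adolescents, although that assumption affects the change-score comparisons and not the factor 1 - r².

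Finally, the general line may simply mean a difference between group means, which would agree with the question-specific text. The change-score reading is plausible mainly for the behaviour scores, because the recoding was done to compute mean scores before and after. The SAP also nowhere says that either test would count as positive, so step 4 is illustrative only. If the simple reading is right, one defining sentence settles the ambiguity, but the missing baseline adjustment remains.

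**Conclusion.** The point holds as a matter of precision and clarity, not validity. It is certain from the text that the question-specific between-arm tests for both primary indices and all three behaviour scores use post-intervention scores alone, that the alternative wording is undefined, and that no analysis adjusts for baseline.

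The size is conditional. With independent students and r between 0.3 and 0.7, the post-only test gives up 9% to 49% of the variance. With allocation by school, the result ranges from a near halving of variance to a small loss, depending on a between-school correlation that the documents do not give. The plan should be changed because the data are already in hand and precision improves in most plausible cases. Naming one primary test also removes a choice that could otherwise be made after seeing results.

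**What to change.** - For CPITN, S-OHI and each behaviour score, name one primary between-arm analysis: the post-intervention score regressed on arm and the baseline score of the same measure. Gender and sampling area may be added.
- State whether students or schools were allocated. If schools, account for school in the model and say whether the school mean of the baseline score is included as well as the student's own score, given step 3.
- Report the adjusted difference with its 95% confidence interval, and keep the unadjusted t-test as a sensitivity analysis.
- Define or delete the mean-differences wording in the Statistical Analyses list and in Question 3, so that both agree with the between-group sections.
- Parts of the SAP are in the past tense, including the statement on missing data, so outcomes may already have been seen. If so, the order changes: report the test now specified and place the adjusted analysis beside it, labelled post hoc.

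The cost is a few lines of SAP text and one regression or mixed model per outcome, with no new data. If the analysis has already been run, it is a re-analysis.

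### The SAP plans no baseline-adjusted between-arm comparison, describes that comparison loosely (in two ways for the behaviour scores), and never ranks it above the paired tests

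*SAP*

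**What the plan says.** **Between-arm test.** The general line under Statistical Analyses in the SAP is "Independent t-tests were used to compare mean differences between the intervention and control groups". The outcome sections are more specific. Question 1, part B, gives the purpose as "To compare the post-intervention CPITN scores between the intervention and control groups", and Question 2, part B, does the same for S-OHI. Question 3 describes the behaviour test twice. Its opening text says "The overall mean differences in oral hygiene practices, dietary habits, and smoking behaviour scores were then compared between groups using independent sample t-tests", after pre and post mean scores have been computed. Its part B gives the purpose as "To compare post-intervention behavioural scores between intervention and control groups".

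**Baseline.** The only remark on baseline within the between-group sections stands under Question 1: "Note: The two groups were examined for their differences in baseline measurement". Neither document plans a covariate-adjusted model.

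**Paired tests.** The general rule, "Paired t-tests will be used to assess within-group differences from baseline to post-intervention", does not restrict them by arm. Question 1 runs them in both arms. Questions 2 and 3 limit them to the intervention arm.

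**Priority.** Each question names group as the independent variable, lists the paired test as part A and the between-group test as part B, and does not say which one answers it. The significance level is 0.05 throughout.

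**Controls.** The Protocol (Data Collection Processes) states that controls received one educational session and the intervention group six.

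**The concern.** There are three linked gaps.

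1. A t-test on follow-up scores and a t-test on change scores are different analyses and can disagree on the same data. If the arms differ at baseline by chance, the post-only test leans towards the arm that started better and the change score towards the arm that started worse.
2. A follow-up comparison adjusted for baseline avoids both leanings and is more precise than either. The data for it are already collected. Checking the arms for baseline differences is not an adjustment, and the SAP does not say what follows if a difference is found.
3. The paired tests carry the same nominal level as the between-arm test and no lower rank. A paired test measures everything that changed over two months: the programme, the single session given to controls, the effect of being examined and interviewed, and regression to the mean. For S-OHI, a primary outcome, and for all behaviours, the outcome sections do not plan even a matching control-arm paired test. A significant paired result could be reported as effectiveness when the arms do not differ.

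**Working it through.** **Inputs.** From the Protocol (sample size paragraph): 536 intervention and 410 control students. From the SAP: significance level 0.05, taken as two-sided. Assumed, because the documents give no values: pre-post correlation r = 0.3, 0.5, 0.7; equal baseline and follow-up variances; allocation by student; shared shift dz = 0.05, 0.10, 0.20. The plan gives no figure of its own on this point to reproduce.

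**Step 1. Paired test in the intervention arm with no programme effect.** Both arms shift by the same dz. The noncentrality is dz × √536 and the test is a two-sided t on 535 degrees of freedom.

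| dz | dz × √536 | P(significant) |
|---|---|---|
| 0.05 | 1.158 | 0.21 |
| 0.10 | 2.315 | 0.64 |
| 0.20 | 4.630 | 0.996 |

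A small change common to both arms is therefore enough to make the paired test significant.

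**Step 2. Precision of the between-arm options.** Variance relative to the post-only test is 2(1 − r) for the change score and 1 − r² for the adjusted comparison. The ratio of adjusted to change score is (1 − r²) / [2(1 − r)] = (1 + r)/2.

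| r | Change / post-only | Adjusted / post-only | Adjusted / change |
|---|---|---|---|
| 0.3 | 1.40 | 0.91 | 0.65 |
| 0.5 | 1.00 | 0.75 | 0.75 |
| 0.7 | 0.60 | 0.51 | 0.85 |

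Apart from one degree of freedom, the adjusted comparison is never less precise than either alternative.

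**Step 3. Error given a chance baseline difference of 1.96 standard errors.** One standard error is √(1/536 + 1/410) = 0.0656 SD, so the difference is 1.96 × 0.0656 = 0.129 SD. With no programme effect and given that difference:

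- post-only Z ~ N(1.96r, 1 − r²);
- change-score Z ~ N(−1.96 √((1 − r)/2), (1 + r)/2).

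| r | P(\|Z\| > 1.96), post-only | P(\|Z\| > 1.96), change score |
|---|---|---|
| 0.3 | 7.9% | 16.0% |
| 0.5 | 12.9% | 12.9% |
| 0.7 | 20.5% | 9.8% |

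The opposite signs of the two means show the opposite leanings. The baseline-adjusted test stays at 5%. Averaged over all possible randomisations, each unadjusted test also has an error of 5%.

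**Step 4. Error if the version is chosen after the results are seen.** The two statistics have correlation √((1 − r)/2) = 0.592, 0.500, 0.387 at r = 0.3, 0.5, 0.7. From the bivariate normal distribution, the chance that at least one is significant is 8.8%, 9.1% or 9.4% two-sided. The chance that at least one falsely shows benefit is 4.4% to 4.7%, against a nominal 2.5%.

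**The case against.** **The two descriptions need not conflict for the primary outcomes.** This stands. The CPITN and S-OHI sections agree on post-intervention scores, a specific section normally governs a general line, and a comparison of mean differences can simply mean the difference in means that any independent t-test estimates. For these two indices the general line is ambiguous. Only Question 3 gives two descriptions of one test.

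**A change score does use baseline.** This also stands. What is missing is a covariate-adjusted model. Subtracting baseline over-corrects for a chance imbalance whenever r is below 1, with equal variances.

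**The unadjusted tests are valid.** This stands under student-level allocation. A reader might infer from Step 3 that the planned tests have inflated error. They do not. The raised rates are conditional on a baseline difference of 1.96 standard errors, and differences at least that large occur in about 5% of such trials.

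**Nothing shows that the version was picked after the results were seen.** Agreed. A reader might infer selective reporting from the loose wording, but the documents do not support that. Step 4 shows what the wording leaves open.

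**The deciding test is implied.** Partly. The variable list "Independent Variable: Group type (Intervention vs. Control") and the objective of evaluating effectiveness both point to the between-arm test. Against that, the questions ask whether sessions reduce scores or improve habits, which a paired result appears to answer, and no sentence ranks the tests. A reader might infer that the trial means to rest its conclusion on the paired tests. The documents do not say that either.

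**Conclusion.** The point holds in a limited form. The plan has a control arm and a between-arm test for every outcome. It lacks a baseline-adjusted model, a single description of the behaviour test, a general line that matches the outcome sections, and a statement that the between-arm comparison decides.

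The most consequential gap is the missing priority, because an assumed shared shift of only dz 0.10 makes the intervention-arm paired test significant 64% of the time with no programme effect. The gain from adjustment is one of precision (9% to 49% less variance than post-only and 15% to 35% less than the change score, for r from 0.3 to 0.7) and of protection against a chance imbalance.

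The correlations and shifts are assumptions. The between-arm figures also assume equal variances and allocation by student. The Protocol's sample size paragraph refers to intervention and control schools, while Data Collection Processes has participants being divided. If schools were allocated, these percentages do not apply as stated. Clustering by school, and multiplicity across CPITN and S-OHI, are separate matters. The change should be made, but its absence does not invalidate the trial.

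**What to change.** 1. State in the SAP that effectiveness on each outcome is judged by one between-arm comparison: the follow-up score adjusted for its own baseline score, reported with a 95% confidence interval. Let this replace the unadjusted independent t-tests in Statistical Analyses and in Questions 1 to 3, which also removes the two descriptions.
2. Report paired tests for both arms on every outcome, labelled descriptive and not as evidence of effectiveness.
3. State whether schools or students were allocated. If schools, the model must also account for school.
4. The SAP is partly in the past tense. If the data have already been analysed, disclose the change as post hoc and show the original t-tests beside the adjusted results.

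**Cost.** No new data are needed. Adjustment uses one degree of freedom per outcome out of about 946 students (536 + 410). If the analysis has been run, the models must be refitted and the post hoc disclosure made.

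### Before-after change is tested in both arms for CPITN but in the intervention arm only for S-OHI and the behaviour scores, in conflict with the SAP's general rules and without a between-arm contrast that clearly uses baseline

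*SAP*

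**What the plan says.** The SAP gives general rules and then a separate plan for each study question.

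- **General rules (SAP, Statistical Analyses).** Within arms: "Paired t-tests will be used to assess within-group differences from baseline to post-intervention". No arm is excluded. Between arms: "Independent t-tests were used to compare mean differences between the intervention and control groups".
- **Question 1, CPITN.** The within-arm test is headed "A. Within-Group Analysis (Intervention group and control group". A note closing this question says that the groups' baseline difference was examined.
- **Question 2, S-OHI.** The within-arm test is headed "A. Within-Group Analysis (Intervention group only", although the same subsection starts from two groups measured twice. The purpose of the between-arm test is "To compare the post-intervention S-OHI scores between the intervention and control groups". There is no baseline note.
- **Question 3, behaviours.** The within-arm test is headed "A. Within-Group Analysis (Intervention Group Only". The stated purpose of the between-arm test is again post-intervention only. The text above it, however, says that the overall mean differences in the behaviour "scores were then compared between groups using independent sample t-tests".

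The SAP names CPITN and S-OHI together as the primary objective and does not explain why they are treated differently. Under Data Collection Processes, the protocol gives control students one session against six, and re-examines and re-interviews participants after two months.

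**The concern.** Question 3 asks whether habits improve after the sessions, and the paired test is given the purpose of detecting exactly that. An uncontrolled before-after test therefore looks like the direct answer to a study question. Scores could move in both arms for reasons unrelated to the six-session programme: every student is examined and interviewed twice, controls also receive a session, and the questionnaire was built around the topics taught (Protocol, Instrument Development). If only the intervention arm's change is shown, the reader cannot see how much of it the control arm shared.

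There is a second gap. If the headings and purpose statements are followed literally, the control arm's baseline S-OHI and behaviour scores enter no test. A difference in starting level between the arms would then carry into the post-intervention comparison. This affects one of two primary indices and all secondary outcomes.

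**Working it through.** **1. The plan side by side**

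| Outcome | Paired test | Stated purpose of between-arm test | Baseline check noted |
|---|---|---|---|
| General rules | no arm limit | mean differences | – |
| CPITN | both arms | post scores | yes |
| S-OHI | intervention only | post scores | no |
| Hygiene, diet, smoking | intervention only | post scores (design text); mean differences (narrative text) | no |

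The specific plans for S-OHI and the behaviours cannot all be followed together with the general rules.

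**2. What the one-arm paired test can show**

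Inputs: n = 536 intervention and 410 control (Protocol, Sample techniques and process; required numbers, not enrolled), two-sided alpha 0.05. The plan gives no figure on this point to reproduce. The documents give no size for shared change and no pre-post correlation r, so both are assumed. Shared change is expressed as dz, the mean change divided by the SD of change. With equal SDs at both visits, the SD of change is SD × √(2(1 − r)). So dz 0.10 equals 0.118 SD at r = 0.3, 0.10 SD at r = 0.5 and 0.077 SD at r = 0.7.

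With no programme effect, the probability of a significant paired test is, by normal approximation,

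1 − Φ(1.96 − dz√n) + Φ(−1.96 − dz√n).

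For n = 536, √n = 23.15. At dz 0.10 this is 1 − Φ(1.96 − 2.315) = Φ(0.355) = 0.64, with a negligible second term.

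| Shared dz | Intervention arm, n = 536 | Control arm, n = 410 |
|---|---|---|
| 0 | 5% | 5% |
| 0.05 | 21% | 17% |
| 0.10 | 64% | 53% |
| 0.15 | 94% | 86% |
| 0.20 | 99.6% | 98% |

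**3. What the between-arm test does with the same change**

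A change common to both arms is added to both post-intervention means and cancels in their difference; it also cancels in the difference of change scores. A simulation with equal baseline means and independent students (5,000 runs per setting; r = 0.3, 0.5, 0.7; dz = 0, 0.10, 0.20) gave rejection rates of 4.5% to 5.5% for post scores and 4.8% to 5.3% for change scores.

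**4. What the post-only test leaves in**

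Suppose the arms start δ SD apart and there is no programme effect. The expected post-intervention difference is rδ if the imbalance is chance and regresses to the mean, and δ if it persists in full. For an assumed δ = 0.10 and r from 0.3 to 0.7, that is 0.03 to 0.07 SD, or 0.10 SD if it persists. The standard error of the post-only difference, with independent students, is √(1/536 + 1/410) = 0.066 SD. An imbalance of this size would therefore move the estimate by about 0.5 to 1.5 standard errors.

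**The case against.** A reader might infer that control-arm change is never estimated for these outcomes. The documents do not support that. The general paired-test line excludes no arm, the general between-arm line can be read as a comparison of change scores, and the Question 3 narrative repeats that wording for the behaviours. For S-OHI only the general section offers this cover. The SAP is thus inconsistent rather than silent, but an analyst who follows the more specific headings would leave the control arm out.

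A reader might also infer that shared drift would be taken for a programme effect in the trial's main comparison. It would not: every affected outcome has a between-arm test, and shared change cancels there (step 3). The 64% and 99.6% describe the one-arm paired test only. They are not false-positive rates of the treatment comparison.

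Three further points stand. The drift sizes are assumptions. Retraining ("Training sessions for the data collectors were held every 15 days throughout the research period") is described as keeping data collection consistent and accurate, so it is a safeguard and not evidence that examiners drifted. And control-arm change is not pure drift, because it includes any effect of the control session.

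Finally, control-arm significance tests would invite comparing p-values across arms. At an identical change of dz 0.10 in both arms, the intervention test is significant and the control test is not in 0.64 × (1 − 0.53) = 30% of trials. This objection shapes the fix.

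**Conclusion.** The point holds as an inconsistency with a practical consequence. For S-OHI and three behaviour scores, the outcome-specific plan sets an uncontrolled before-after test beside a between-arm test described on post scores alone, and the general rules say something different. The paired test cannot support a claim of effect: under an assumed shared change of dz 0.10 to 0.20 and no programme effect, it is significant in 64% to 99.6% of trials at n = 536. At dz 0.05 the figure is 21%.

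The between-arm conclusion is not biased by shared change. What the post-only form leaves open is baseline imbalance, of unknown size here. All calculations treat students as independent, so they make no allowance for clustering by school.

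**What to change.** In the SAP:

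1. Under Questions 2 and 3, replace the intervention-only limit on the within-arm analysis with both arms, as for CPITN.
2. For every outcome, tabulate mean change with 95% CI in both arms side by side, labelled as description and not as evidence of effect.
3. Name one between-arm contrast that uses baseline and apply it to every outcome: either the post-intervention difference adjusted for baseline, or the difference in change scores, which fits the general rule on mean differences. The residual variance relative to a post-only comparison is 1 − r² for the first and 2(1 − r) for the second; at an assumed r = 0.5 these are 0.75 and 1, so baseline adjustment is the more precise.
4. Reword the post-only purpose statements under all three questions to match that contrast, and state that no within-arm test supports the conclusion.

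The cost is SAP wording and four extra table rows (control-arm change for S-OHI, hygiene, diet and smoking). The protocol already collects these data. The small downside is that within-arm results may be misread by comparing p-values across arms; items 2 and 4 are there to prevent that.
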